### **6 TRIAL TREATMENTS**

Trial treatment is defined as any investigational treatment(s), marketed product(s), intended to be administered to a trial subject according to the trial protocol.

## 6.1 IMPs administered

IMP name:	
 
• BNT162b2
 
• BNT162b2 (B.1.1.7 + B.1.617.2)
 
• BNT162b2 (B.1.1.7)
 
• BNT162b2 (B.1.617.2)
 
• BNT162b2 (B.1.1.529)
 

Type:	Vaccine (BNT162 RNA-LNP vaccine utilizing modRNA).
Use:	Experimental
Administration route:	Intramuscular (IM); upper arm, musculus deltoideus. The same arm may be used for both immunizations. The non-dominant arm is preferred.
Dosing regimen:	
Part A:
 
 
• Cohort 1: One dose of 30 µg BNT162b2 (B.1.1.7 + B.1.617.2), consisting of a 1:1 mixture of 15 µg BNT162b2 (B.1.1.7) and 15 µg BNT162b2 (B.1.617.2), given on Day 1.
 
• Cohort 2: Two doses of 30 µg BNT162b2 (B.1.1.7 + B.1.617.2), one each on Day 1 and Day 56.
 
• Cohort 3: One dose of 30 µg BNT162b2 (B.1.1.7) on Day 1.
 
• Cohort 4: One dose of 30 µg BNT162b2 (B.1.617.2) on Day 1.
 
• Cohort 5: One dose of 30 µg BNT162b2 on Day 1.
 
• Cohort 6: Three doses (on Day 1, Day 21, and the third dose ~6 months after the second dose) of 30 µg BNT162b2 (B.1.1.7 + B.1.617.2).
 
 
Part B:
 
 
• Cohort 1: One (on Day 1) dose of 30 µg BNT162b2 (B.1.1.7 + B.1.617.2).
 
• Cohort 4: One (on Day 1) dose of 30 µg BNT162b2 (B.1.617.2).
 
• Cohort 6: Three doses (on Day 1, Day 21, and the third dose ~6 months after the second dose) of 30 µg BNT162b2 (B.1.1.7 + B.1.617.2).
 
 
Part C:
 
 
• Cohort 7: One dose of 30 µg BNT162b2 (B.1.1.529) on Day 1.
 
• Cohort 8: One dose of 30 µg BNT162b2 on Day 1.
 
• Cohort 9: No IMP injection within 3 months of Visit 1.
 

Sourcing:	Provided centrally by the sponsor.
Packaging and labeling:	IMP will be provided in glass vials as open-label supply. Each vial will be labeled as required per country requirements. For details, see the Pharmacy Manual.

Note: BNT162b2 (B.1.1.529) refers to the monovalent vaccine specific for SARS-CoV-2 Omicron subvariant BA.1, i.e., B.1.1.529.1.

## 6.2 Preparation/handling/storage/accountability

The principal investigator is responsible for IMP (and any components thereof) accountability, reconciliation, and record maintenance (i.e., receipt, reconciliation, and final disposition records).

For instructions on IMP preparation, handling, and storage, see the Pharmacy Manual.

All IMPs (and any components thereof) must be stored in a secure, environmentally controlled, and monitored (manual or automated) area in accordance with the labeled storage conditions with access limited to the investigator and authorized trial site personnel.

The preparation of solution for injection will be performed by aseptic handling procedures by pharmaceutical personnel or other trained personnel at the trial site. Further guidance and information for the final disposition of unused IMP (and any components thereof) is provided in the Pharmacy Manual.

### **6.3 Measures to minimize bias: randomization and blinding**

Laboratory personnel who will analyze the samples to generate immunogenicity data for the primary and secondary immunogenicity endpoints in Part B will be blinded to the source of samples (BNT162-17 vs BNT162-02 / C4591001) or the actual treatment.

Randomization will be applied to Part C of the trial only. At randomization, subjects will be stratified by the following factors: age group (18 to 55 years of age or 56 to 85 years of age); number of prior doses of RNA-based vaccines (two or three doses).

### **6.4 Trial treatment compliance**

All IMP injections will be administered by a physician or by qualified medical personnel.

The date and time of each IMP injection must be recorded in the source documents and recorded in the case report form (CRF). The IMP dose and trial subject identification will be confirmed at the time of administration by a member of the trial site personnel other than the person administering the IMP.

### **6.5 Concomitant therapy**

#### **6.5.1 Permitted concomitant therapies**

For healthy volunteers with pre-existing stable disease, defined as disease not requiring significant change in therapy or hospitalization for worsening disease during the 12 weeks before Visit 0, the continued use of the ongoing stable therapy is allowed.

The use of antipyretics and other pain medication to treat symptoms after IMP administration or for ongoing conditions is permitted, but not for prophylaxis. See the guidance on antipyretics and other pain medication in Section [6.5.2](#).

Inhaled, topical, or localized injections of corticosteroids (e.g., intraarticular or intrabursal administration) are permitted.

Administration of nonsteroidal anti-inflammatory drugs (NSAIDs), e.g., paracetamol/acetaminophen at doses of up to 4 g/day, is permitted to treat symptoms after IMP administration or for ongoing conditions (but not for prophylaxis). Other concomitant medication may be considered on a case by case basis by the investigator, if required after consultation with the sponsor's Medical Monitor.

### **6.5.2 Prohibited concomitant therapies**

Trial subjects should not receive any live or live attenuated vaccination within 28 days before or after any IMP injection, e.g., measles, mumps, and rubella (MMR); oral polio vaccine (OPV); varicella; yellow fever unless medically indicated. See [exclusion criteria 11](#).

Trial subjects should not receive any other vaccines within 14 days before or after any IMP injection, e.g., influenza, tetanus, pneumococcal, hepatitis A or B. When possible, standard or care vaccinations should be planned with the trial IMP administrations in mind. See [exclusion criteria 12](#).

Trial subjects should not receive treatment with radiotherapy or immunosuppressive therapy, including cytotoxic agents or systemic corticosteroids (if systemic corticosteroids are administered for  $\geq 14$  days at a dose of  $\geq 20$  mg/day of prednisone or equivalent), e.g., for cancer or an autoimmune disease, or planned receipt throughout this trial. Inhaled/nebulized, intraarticular, intrabursal, or topical (skin or eyes) corticosteroids are permitted. See [exclusion criteria 13](#).

Receipt of blood/plasma products or immunoglobulins from Visit 0 or planned receipt throughout this trial. See [exclusion criteria 14](#).

Trial subjects should not receive any non-trial SARS-CoV-2 vaccine during the BNT162-17 trial.

Trial subjects should not receive prophylactic antipyretics and other pain medication to prevent symptoms associated with IMP administration. However, if a trial subject is taking a medication for another condition, even if it may have antipyretic or pain-relieving properties, it should not be withheld prior to IMP administration in this trial.

Trial subjects should not receive prophylactic medications intended to prevent symptoms associated with COVID-19. However, if a trial subject is taking a medication for another condition, even if it may have such properties, this does not exclude the volunteer from enrollment into this trial.

### **6.5.3 Recording of concomitant therapy**

Any medication or vaccine (including over-the-counter or prescription medicines, vitamins, and/or herbal supplements, or other specific categories of interest) that the trial subject receives from Visit 0 until Visit 1, and for 1 month after each IMP dose (at the times listed in the SoA, Section [1.3](#)), and any medications due to medical history started before Visit 0 (i.e., prior medication) must be recorded in the CRF along with the:

- Reason for use
- Dates of administration including start and end dates
- Dosage information including dose and frequency

Prohibited medications should be recorded in the CRF for the whole duration of trial subject participation in the trial.

## 6.6 Dose modifications

In Part A, for Cohorts 1 to 4, an optional additional lower dose level may be tested in up to 20 additional subjects per cohort.

## 6.7 Access to trial treatment after the end of the trial

Not applicable.

# 7 DISCONTINUATION OF TRIAL TREATMENT AND TRIAL SUBJECT DISCONTINUATION/WITHDRAWAL

## 7.1 Discontinuation of trial treatment

### 7.1.1 *Criteria to permanently discontinue IMP administration*

Note that discontinuation from IMP does not represent withdrawal/discontinuation from the trial. Trial subjects permanently discontinued from IMP administration should still complete all assessments planned in the SoA (Section 1.3).

Reasons for definitive discontinuation from IMP include the following:

- SAEs warranting discontinuation;
- other trial-related safety concerns;
- subject or investigator request;
- pregnancy;
- deterioration in trial subject health at the time of IMP injection (at the discretion of the investigator).

In the event of trial subject permanent discontinuation from IMP, it must be documented on the appropriate CRF/in the medical records if the trial subject is discontinuing further receipt of trial treatment, or also from trial procedures, post-treatment follow-up, future collection of additional information and/or consent.

### 7.1.2 *Criteria for temporarily delaying enrollment or administration of IMP*

There are no criteria defined which trigger temporarily delaying trial subject enrollment.

There are medical conditions or situations which may delay administration of IMP as follows:

- Current febrile illness (body temperature  $\geq 38.0^{\circ}\text{C}/\geq 100.4^{\circ}\text{F}$ ) or other acute illness within 48 h before any IMP administration. This includes current symptoms that could represent a potential COVID-19 illness.
- The second IMP injection may also be delayed for medical reasons (e.g., influenza vaccination) and such delays should be as short as possible, e.g.,  $\leq 3$  weeks for non-live or attenuated vaccines,  $\leq 5$  weeks for live attenuated vaccines,  $\leq 12$  weeks if SARS-CoV-2 infection is confirmed, etc.

The circumstances leading to any delayed administration of IMP and the resulting delay should be discussed with the sponsor's Medical Monitor.

## **7.2 Trial subject discontinuation or withdrawal from the trial**

A trial subject may withdraw from the trial at any time at his/her own request or may be discontinued from the trial at any time at the discretion of the investigator for safety, behavioral, compliance, or administrative reasons. Withdrawals are expected to be uncommon.

Reasons for discontinuation from the trial include the following:

- Refused further trial procedures
- Lost to follow-up
- Death
- Trial terminated by sponsor
- Trial subject request
- Investigator request
- Important protocol deviation per the investigator after consultation with the Medical Monitor
- Receipt of non-trial SARS-CoV-2 vaccination during the trial

If the trial subject withdraws consent for data processing, the sponsor may retain and continue to use any data collected before such a withdrawal of consent.

For trial subjects who withdraw consent, the investigator must clarify whether consent for research sample storage/processing (if given) is also withdrawn. If yes, then they must be informed that any research samples collected will be destroyed. The investigator must document research sample destruction in the Investigator's Site File (ISF) and inform the sponsor about the withdrawal of consent immediately.

If possible, permanently discontinued trial subjects will complete all assessments planned for the Early Termination Visit.

## **7.3 Lost to follow-up**

A trial subject will be considered lost to follow-up if they repeatedly fail to return for scheduled visits and is unable to be contacted by the trial site.

The following actions must be taken if a trial subject fails to return to the trial site for a required trial visit:

- The trial site must attempt to contact the trial subject and reschedule the missed visit as soon as possible and counsel the trial subject on the importance of maintaining the assigned visit schedule and ascertain whether or not the trial subject wishes to continue in the trial.

- Before a trial subject is deemed lost to follow-up, the investigator or designee must make every effort to regain contact with the trial subject (where possible, three telephone calls and, if necessary, a certified letter to the trial subject's last known mailing address or local equivalent methods). These contact attempts should be documented in the trial subject's medical record.
- If the trial subject continues to be unreachable, they will be considered to have withdrawn from the trial.

#### **7.4 Replacement of permanently discontinued trial subjects**

Permanently discontinued trial subjects will not be replaced.

### **8 TRIAL ASSESSMENTS AND PROCEDURES**

Trial subjects must have given informed consent (i.e., have signed the ICF) before initiation of any trial-specific procedures are performed.

Protocol waivers or exemptions are not allowed.

Immediate safety concerns should be discussed with the sponsor immediately upon occurrence or awareness to determine if the trial subject should continue or discontinue IMP administration.

Adherence to the trial protocol requirements, including those specified in the SoA, is essential and required for trial conduct.

All screening evaluations must be completed and reviewed to confirm that potential trial subjects meet all eligibility criteria. The investigator will maintain a screening log to record details of all trial subjects screened and to confirm eligibility or record reasons for screening failure, as applicable.

See the SoA (Section 1.3) for all planned time points for assessments.

#### **8.1 Efficacy assessments**

Not applicable.

#### **8.2 Safety assessments**

Planned time points for all safety assessments are provided in the SoA (Section 1.3).

##### **8.2.1 Clinical assessment**

###### **8.2.1.1 Physical examinations including body weight**

Body weight (in kg or pounds) will be measured and recorded at screening.

Subject height (in cm or inches) will be measured and recorded.

Complete and symptom-orientated physical examinations will be performed at the time points listed in the SoA in Section 1.3.

- A (complete) physical examination will include, at a minimum, assessments of the cardiovascular, respiratory, gastrointestinal, and neurological systems.
- A symptom-orientated physical examination includes an overall health judgment.

#### **8.2.1.2 Vital signs**

Vital signs comprising oral body temperature, heart rate, and blood pressure (systolic and diastolic) will be assessed at the times given in the SoA (Section 1.3).

Blood pressure and heart rate measurements will be assessed with a completely automated device. Manual techniques will be used only if an automated device is not available.

Vitals signs measurements should be preceded by at least 5 minutes of rest for the trial subject in a quiet setting without distractions (e.g., television, cell phones).

Vital signs will be measured with trial subjects in seated position.

#### **8.2.1.3 Clinical laboratory tests**

See Section 10.2 for the list of clinical laboratory tests to be performed at baseline and the limited times given in the SoA (Section 1.3).

All protocol-required clinical laboratory tests (see Section 10.2) must be conducted in accordance with the local laboratory standard. The investigator must review the laboratory report, document this review with signature and date.

If laboratory values from non-protocol-specified laboratory assessments performed at the laboratory require a change in trial subject management or are considered clinically significant by the investigator (e.g., SAE, AE), then the results must be recorded in the CRF.

#### **8.2.1.4 Electrocardiograms**

Standard 12-lead ECGs will be recorded at the times given in the SoA (Section 1.3) using an ECG machine that automatically calculates the heart rate and measures PR, QRS, QT, and corrected QT (QTc; according to Bazett) intervals.

All ECGs will be judged by the investigator as clinically significant (yes/no); only the investigator assessment, description of abnormalities, and heart rate will be recorded in the CRF.

For reporting and surveillance purposes, all ECGs may be forwarded to a central vendor for assessment.

#### **8.2.2 Oral body temperature (in °C or °F)**

Oral body temperature (in °C or °F) will be assessed at the times given in the SoA (Section 1.3). Body temperature will be measured and recorded to one decimal place. Body temperature will be converted to °C for reporting.

### 8.2.3 **Subject e-diaries for assessment of reactogenicity (local and systemic reactions)**

Subject e-diaries will be issued, trained, and collected by trial site personnel at the visits given in the SoA (Section 1.3).

The trial site personnel will remind the subject to record the worst grade for each symptom in the e-diary at approximately the same time every evening on the day of IMP injection and then every day in the evening for a total of seven consecutive days.

The trial site personnel will remind the subject to measure their oral body temperature using the provided thermometer or device and record their oral body temperature in the e-diary every day including the day of IMP injection.

The reporting on the CRF of local and systemic reactions will be based on the subject's assessments only.

The trial site personnel should review daily the e-diary entries of their trial subjects.

All reported Grade 4 local and/or systemic reactions must be confirmed by an investigator or a medically qualified person.

The grading of reported solicited local and systemic reactions will be performed using the grading scale tables given in Sections 8.2.3.1 and 8.2.3.2, which are based on the FDA Guidance for Industry "[Toxicity Grading Scale for Healthy Adult and Adolescent Volunteers Enrolled in Preventive Vaccine Clinical Trials](#)".

#### 8.2.3.1 **Assessments of intensity for local reactions**

Redness and swelling/induration will be measured and recorded in centimeters or inches and then categorized during analysis as absent, mild, moderate, severe or potentially life-threatening, based on the grading scale in Table 9. Likewise, pain (perceived) and tenderness (elicited) at the injection site will be assessed by the trial subject as absent, mild, moderate, severe, or potentially life-threatening, according to the grading scale in Table 9.

**Table 9: Local reaction grading scale**

	Mild (Grade 1)	Moderate (Grade 2)	Severe (Grade 3)	Potentially life-threatening (Grade 4)
Pain at the injection site	Does not interfere with activity	Interferes with activity	Prevents daily activity	Emergency room visit or hospitalization for severe pain
Tenderness	Mild discomfort to touch	Discomfort with movement	Significant discomfort at rest	Emergency room visit or hospitalization
Erythema/rednessa	2.5 cm to 5.0 cm (0.98 in to 1.96 in)	>5.0 cm to 10.0 cm (>1.96 in to 3.94 in)	>10 cm (>3.94 in)	Necrosis or exfoliative dermatitis
Induration/swellingb	2.5 cm to 5.0 cm (0.98 in to 1.96 in)	>5.0 cm to 10.0 cm (>1.96 in to 3.94 in)	>10 cm (>3.94 in)	Necrosis

a. In addition to grading the measured local reaction at the greatest single diameter, the measurement should be recorded as a continuous variable.

b. Induration/swelling should be evaluated and graded using the functional scale as well as the actual measurement.

### 8.2.3.2 Assessments of intensity for systemic reactions

#### *Symptoms of systemic reactions*

Symptoms of systemic reactions will be assessed by the trial subject as absent, mild, moderate, severe, or potentially life-threatening, according to the grading scale in [Table 10](#).

If a fever of  $\geq 39.0^{\circ}\text{C}/\geq 102.1^{\circ}\text{F}$  is recorded by a subject during the 7-day post-injection e-diary period, a telephone contact should occur to ascertain further details and determine whether a site visit is clinically indicated. Only an investigator or medically qualified person is able to confirm a trial subject's fever as  $>40.0^{\circ}\text{C}/>104.0^{\circ}\text{F}$  for recording in the trial database. If a trial subject experiences a confirmed fever  $>40.0^{\circ}\text{C}/>104.0^{\circ}\text{F}$ , the investigator must immediately notify the sponsor and, if it is determined to be related to the administration of IMP, further IMP injections will be discontinued in that trial subject.

**Table 10: Systemic reaction grading scale**

	Mild (Grade 1)	Moderate (Grade 2)	Severe (Grade 3)	Potentially life- threatening (Grade 4)
Fever (oral temperature of <math>\geq 38.0^{\circ}\text{C}/\geq 100.4^{\circ}\text{F}</math>)	$\geq 38.0^{\circ}\text{C}/\geq 100.4^{\circ}\text{F}$ to $38.4^{\circ}\text{C}/101.1^{\circ}\text{F}$	$\geq 38.5^{\circ}\text{C}/\geq 101.2^{\circ}\text{F}$ to $38.9^{\circ}\text{C}/102.0^{\circ}\text{F}$	$\geq 39.0^{\circ}\text{C}/\geq 102.1^{\circ}\text{F}$ to $40.0^{\circ}\text{C}/104.0^{\circ}\text{F}$	$>40.0^{\circ}\text{C}/>104.0^{\circ}\text{F}$
Vomiting	1 to 2 times in 24 h	>2 times in 24 h	Requires intravenous hydration	Emergency room visit or hospitalization for hypotensive shock
Diarrhea	2 to 3 loose stools in 24 h	4 to 5 loose stools in 24 h	6 or more loose stools in 24 h	Emergency room visit or hospitalization for severe diarrhea
Headache	Does not interfere with activity	Some interference with activity	Prevents daily routine activity	Emergency room visit or hospitalization for severe headache
Fatigue/tiredness	Does not interfere with activity	Some interference with activity	Prevents daily routine activity	Emergency room visit or hospitalization for severe fatigue
Chills	Does not interfere with activity	Some interference with activity	Prevents daily routine activity	Emergency room visit or hospitalization for severe chills
Nausea	No interference with activity or 1 to 2 episodes/24 h	No interference with activity or >2 episodes/24 h	Prevents daily activity, requires outpatient intravenous hydration	Emergency room visit or hospitalization for hypotensive shock
New or worsened muscle pain	Does not interfere with activity	Some interference with activity	Prevents daily routine activity	Emergency room visit or hospitalization for severe new or worsened muscle pain
New or worsening joint pain	Does not interfere with activity	Some interference with activity	Prevents daily routine activity	Emergency room visit or hospitalization for severe new or worsened joint pain

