3.1.1.1 Local reactions

The local reactions assessed by trial subjects and reported in the e-diary are pain at the injection site, tenderness, erythema/redness, induration/swelling, from Day 1 through Day 7 after each trial IMP dose, where Day 1 is the day of each IMP injection. A subject is deemed to have had a local reaction if they report the reaction as “yes” on any day of the e-diary recording period (i.e., Day 1 through Day 7 inclusive).

For redness and swelling, the reported size must be at least 2.5 cm (0.98 inches) to be deemed as a local reaction. Redness and swelling with a size less than 2.5 cm will not be included in the analysis.

Solicited local reactions will be categorized as mild, moderate, severe, or potentially life-threatening) and graded from 1 to 4, during the analysis as described in Table 5. The categories and grades are based on the FDA Guidance for Industry: [“Toxicity Grading Scale for Healthy Adult and Adolescent Volunteers Enrolled in Preventive Vaccine Clinical Trials”](#).

Table 5. Local reaction grading scale

	Mild (Grade 1)	Moderate (Grade 2)	Severe (Grade 3)	Potentially life-threatening (Grade 4)
Pain at the injection site	Does not interfere with activity	Interferes with activity	Prevents daily activity	Emergency room visit or hospitalization for severe pain
Tenderness	Mild discomfort to touch	Discomfort with movement	Significant discomfort at rest	Emergency room visit or hospitalization
Erythema /redness ^a	2.5 cm to 5.0 cm (0.98 in to 1.96 in)	>5.0 cm to 10.0 cm (>1.96 in to 3.94 in)	>10 cm (>3.94 in)	Necrosis or exfoliative dermatitis
Induration /swelling ^b	2.5 cm to 5.0 cm (0.98 in to 1.96 in)	>5.0 cm to 10.0 cm (>1.96 in to 3.94 in)	>10 cm (>3.94 in)	Necrosis

- a) In addition to grading the measured local reaction at the greatest single diameter, the measurement should be recorded as a continuous variable.
- b) Induration/swelling should be evaluated and graded using the functional scale as well as the actual measurement.

For subjects recording at least one local reaction from Day 1 through Day 7 after IMP injection:

- The maximum severity grade is equal to the highest graded local reaction within the recording period.

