3.1.1.2 Systemic events

Symptoms of systemic events assessed by trial subjects and recorded in the e-diary are fever, fatigue, headache, chills, vomiting, nausea, diarrhea, new or worsened muscle pain, and new or worsening joint pain from Day 1 through Day 7 inclusive, where Day 1 is the day of each IMP injection. The derivations for systemic events will be handled similar to the way local reactions are handled for presence of an event, severity level, duration, and onset day.

Fever is defined as an oral temperature $\geq 38.0^{\circ}\text{C}$ (100.4°F). Temperatures collected in degrees Fahrenheit will be converted to degrees Celsius using $(^{\circ}\text{F} - 32) \times 5/9$ and grading will be based on the unrounded conversions. An investigator or medically qualified person

must confirm a trial subject's fever as $>40.0^{\circ}\text{C}/>104.0^{\circ}\text{F}$ before it is entered in the trial database.

The highest oral temperature for each day will be recorded in the e-diary and the maximum temperature from Day 1 through Day 7 will be graded as described in [Table 6](#).

Solicited systemic events will be categorized as mild, moderate, severe, or potentially life-threatening) and graded from 1 to 4, during the analysis as described in [Table 6](#).

Table 6. Systemic events grading scale

	Mild (Grade 1)	Moderate (Grade 2)	Severe (Grade 3)	Potentially life-threatening (Grade 4)
Fever (oral temperature of $\geq 38.0^{\circ}\text{C}/\geq 100.4^{\circ}\text{F}$)	$\geq 38.0^{\circ}\text{C}/\geq 100.4^{\circ}\text{F}$ to $38.4^{\circ}\text{C}/101.1^{\circ}\text{F}$	$\geq 38.5^{\circ}\text{C}/\geq 101.2^{\circ}\text{F}$ to $38.9^{\circ}\text{C}/102.0^{\circ}\text{F}$	$\geq 39.0^{\circ}\text{C}/\geq 102.1^{\circ}\text{F}$ to $40.0^{\circ}\text{C}/104.0^{\circ}\text{F}$	$>40.0^{\circ}\text{C}/>104.0^{\circ}\text{F}$
Vomiting	1 to 2 times in 24 h	>2 times in 24 h	Requires intravenous hydration	Emergency room visit or hospitalization for hypotensive shock
Diarrhea	2 to 3 loose stools in 24 h	4 to 5 loose stools in 24 h	6 or more loose stools in 24 h	Emergency room visit or hospitalization for severe diarrhea
Headache	Does not interfere with activity	Some interference with activity	Prevents daily routine activity	Emergency room visit or hospitalization for severe headache
Fatigue/tiredness	Does not interfere with activity	Some interference with activity	Prevents daily routine activity	Emergency room visit or hospitalization for severe fatigue

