Chills	Does not interfere with activity	Some interference with activity	Prevents daily routine activity	Emergency room visit or hospitalization for severe chills
Nausea	No interference with activity or 1 to 2 episodes/24 h	No interference with activity or >2 episodes/24 h	Prevents daily activity, requires outpatient intravenous hydration	Emergency room visit or hospitalization for hypotensive shock
New or worsened muscle pain	Does not interfere with activity	Some interference with activity	Prevents daily routine activity	Emergency room visit or hospitalization for severe new or worsened muscle pain

	Mild (Grade 1)	Moderate (Grade 2)	Severe (Grade 3)	Potentially life- threatening (Grade 4)
New or worsening joint pain	Does not interfere with activity	Some interference with activity	Prevents daily routine activity	Emergency room visit or hospitalization for severe new or worsened joint pain

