6.1.1.2 Local reactions

The number and percentage of subjects reporting local reactions (pain at the injection site, tenderness, erythema/redness, induration/swelling) within 7 days after each dose will be

summarized by maximum severity and cumulatively across severity levels. The associated 2-sided Clopper-Pearson 95% CI's will also be displayed.

The Reactogenicity Set will be used for local reaction summaries. Subjects without any e-diary data throughout the 7 days after vaccination or have recorded events only beyond 7 days, will be excluded from the local reaction analysis.

In addition, local reactions will also be summarized by:

- Duration (days) of each local reaction after each dose.
- Onset day of each local reaction after each dose.

Bar charts with the proportions of subjects for each local reaction throughout 7 days after each dose will be plotted. The bars will be divided into severity categories to highlight the proportions of subjects by maximum severity. In addition, listing of subjects in the Reactogenicity Set, with reported local reactions, will be provided.

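### The nausea row of the grading scale gives Grades 1 and 2 the same activity criterion, so the mild/moderate split for nausea is not defined as printed

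*Protocol*

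**What the plan says.** Protocol Section 8.2.3.2 has the subject apply the scale: "Symptoms of systemic reactions will be assessed by the trial subject as absent, mild, moderate, severe, or potentially life-threatening". In Protocol Table 10, and word for word in SAP Table 6 (Section 3.1.1.2), nausea is graded as follows:

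- Grade 1: "No interference with activity or 1 to 2 episodes/24 h"
- Grade 2: "No interference with activity or >2 episodes/24 h"
- Grade 3: "Prevents daily activity, requires outpatient intravenous hydration"

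Headache, fatigue, chills, muscle pain and joint pain have no interference at Grade 1 and "Some interference with activity" at Grade 2.

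SAP Section 3.1.1.2 also says that systemic events are categorized during the analysis by Table 6, and that "The derivations for systemic events will be handled similar to the way local reactions are handled". For local reactions, Section 3.1.1.1 states: "The maximum severity grade is equal to the highest graded local reaction within the recording period". SAP Section 6.1.1.2 has local reactions "summarized by maximum severity and cumulatively across severity levels", and Section 6.1.1.3 extends that layout to systemic events.

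**The concern.** A severity scale should send each event to one grade. Here the activity clause is identical in two adjacent grades, and *or* makes that clause sufficient by itself in each. A single mild episode that does not disturb the subject's day satisfies the printed criteria for both mild and moderate. Partial interference, which marks moderate in the comparable rows, does not appear in the nausea row at all.

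At stake is whether moderate nausea in the reactogenicity tables and bar charts means the same thing for every subject, and the same thing as moderate headache or fatigue. Nausea is a solicited systemic event for every vaccinated cohort in Parts A, B and C, so the row is used throughout the trial.

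**Working it through.** No power, alpha or sample-size figure is involved. The check is to list the possible events and read the printed row literally.

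**Step 1: the row as printed.** Cross activity level with episodes per 24 hours. The last two columns show what each possible precedence rule would give. The SAP states neither rule.

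| Activity | Episodes | Meets Grade 1 by | Meets Grade 2 by | If the higher match is taken | If the lower match is taken |
|---|---|---|---|---|---|
| none affected | 1–2 | activity and count | activity | 2 | 1 |
| none affected | >2 | activity | activity and count | 2 | 1 |
| partly affected | 1–2 | count | – | 1 | 1 |
| partly affected | >2 | – | count | 2 | 2 |

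Both unaffected-activity cells meet two grades. Neither partly-affected cell has a grade based on activity. Taking the higher match also inverts the order at one to two episodes: nausea that leaves activity untouched would be Grade 2, and nausea that partly limits it would be Grade 1. Reading the episode count alone gives a consistent split (1, 2, 1, 2 down the rows), but the printed text does not say to ignore the activity clause.

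**Step 2: comparison with neighbouring rows.** Five of the six activity-graded systemic rows move from no interference, to some, to prevention of routine activity. Nausea alone repeats its Grade 1 clause at Grade 2. The general intensity scale in Protocol Section 10.3.1.7 also puts partial interference at Grade 2, but it applies only to terms without specific guidance, so it does not resolve the row. The SAP carries identical wording, so a text-extraction fault is unlikely.

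**Step 3: which outputs use the boundary.** The primary safety estimand is the percentage of subjects reporting systemic events within seven days of each dose; it contains no grade. Protocol Section 9.4.2 asks for any-grade and Grade 3 or higher summaries of systemic reactions and names worst grade only for local reactions. Onset day in the SAP is the first day of any severity. The Grade 1/Grade 2 boundary for nausea enters through SAP Section 6.1.1.3, in the maximum-severity tables, any cumulative row that starts or stops at that boundary, and the matching bar charts.

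**Step 4: how many subjects.** The scale applies to a planned 120 (Part A) + 1,125 (Part B) + 90 + 90 (Cohorts 7 and 8, Protocol Section 9.2.3) = 1,425. Protocol Section 2.3.1 lists nausea with the parent vaccine at 1/100 to under 1/10. *Assuming* that rate held here, any nausea would be reported by between 1,425 × 0.01 ≈ 14 and 1,425 × 0.10 ≈ 142 subjects. Solicited diary rates over one to three doses may differ. The share of these that is ambiguous, and the share misgraded, cannot be derived.

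**The case against.** The strongest defence is that the episode counts do not overlap: one to two against more than two, the same division as the vomiting row. A sensible subject would let frequency decide, and even a partly limiting bout can be counted and graded. That stands as a limit on the practical effect. It does not make the row correct, because the activity clause is printed as a sufficient criterion in both cells.

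Several stronger readings are tempting, and the documents do not support them:

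- *That the SAP's maximum-severity rule turns all nausea without interference into moderate.* The rule takes the highest grade recorded over Days 1 to 7. It does not choose between two cells matched by the same event.
- *That nausea with some interference cannot be graded.* It can, by count. What it lacks is a grade based on activity.
- *That a primary result is compromised.* Step 3 shows that the estimand carries no grade. The safety objectives are descriptive, and hypotheses are tested only for Part B immunogenicity.
- *That 1,425 subjects are affected.* That is the planned number to whom the scale applies.

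It is also fair to object that new table wording cannot repair collected data. SAP Section 8.3 records that the trial ended on 04 October 2023 and that a protocol amendment was no longer possible. That objection stands and shapes the fix.

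**Conclusion.** The point holds as a wording error carried through two tables. As printed, Grades 1 and 2 of nausea are not mutually exclusive and skip partial interference, and nothing else in either document supplies a rule. The consequence is narrow: the mild/moderate division of nausea in the SAP's severity summaries cannot be interpreted unless the e-diary used clearer text. The any-nausea percentage and Grades 3 and 4 are unaffected, because their wording is not part of the duplication. No count of misclassified subjects can be given.

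The conclusion assumes that *or* is read as written and that the printed row may have been the one used. The documents show neither the fielded e-diary text nor any programmed grading algorithm. If the e-diary offered an unambiguous nausea item, the data are sound and only the tables are wrong.

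**What to change.** **For any future use of the scale:** reword Grade 2 nausea as "Some interference with activity" or more than two episodes in 24 hours, in line with the other rows. Add a sentence saying which grade applies when activity and count point to different grades. The *or* still leaves two such cells: unaffected activity with more than two episodes, and partly affected activity with one to two.

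**For this trial:** retrieve the nausea wording fielded in the e-diary and state in the SAP and the report how the grade was assigned.

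- If the wording was unambiguous, correct SAP Table 6 to match it and report the split as planned.
- If it was the printed text, do not regrade what subjects chose. Present nausea Grades 1 and 2 combined, or keep the split but flag it as not distinguishable, with a footnote in the SAP and the report. Leave the any-nausea and Grade 3 or higher rows as they are.

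The cost is one check of the e-diary text, a table correction or a pooled row, and a footnote. The downside of pooling is the loss of one prespecified descriptive severity level for nausea, which makes that row less detailed than the others.
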